2.2 DISPOSITION OF PATIENTS

This section describes patient disposition for both patient study status and the patient analysis populations.

Screened patients are defined as all patients who have signed the informed consent.

Randomized patients consist of all patients who have signed informed consent, with a randomized open-label treatment kit allocated and recorded in the IRT database, regardless of whether the treatment kit was actually used or not.

For patient study status, the total number of patients in each of the following categories will be presented in the clinical study report (CSR), using a flowchart diagram or summary table:

- Screened patients
- Screen failure patients and reasons for screen failure
- Nonrandomized but treated patients
- Randomized patients
- Randomized but not treated patients
- Randomized and treated patients
- Patients who have completed the 26-week randomized treatment period as per protocol
- Patients who have completed the whole study treatment period including 26-week single-arm extension period
- Patients who permanently discontinued the IMP during the 26-week randomized treatment period, and the reasons for treatment discontinuation.
- Patients who permanently discontinued the IMP during the 26-week single-arm extension period, and the reasons for treatment discontinuation (for FRC group only).
- Patients who completed/discontinued the study,
- Patients' end of study status (completed, not completed) by end of treatment status (completed, not completed),

- Status at last study contact.

For the screened, screen failure, and non-randomized but treated patients, percentages will be calculated using the number of screened patients as the denominator. All other categories of patients will be presented by treatment group, and percentages will be calculated using the number of randomized patients within each treatment group as the denominator. Reasons for treatment discontinuation will be provided in tables giving numbers and percentages by treatment group.

A summary of the distribution of patients by country and center will also be provided (overall number of patients screened, screened but not randomized, randomized, and randomized but not treated, and number of patients randomized and discontinued from study treatment for each treatment group).

Patients treated but not randomized, patients randomized but not treated and patients randomized but not treated as randomized will be identified and described in separate listings. Only the patients of the third category (randomized and not treated as randomized) will be part of efficacy and safety analyses (see [Section 2.3](#)). Safety data of patients treated but not randomized will be reported separately.

The randomization strata [HbA1c at Visit 1 (<8%, ≥8%) and GLP-1 receptor agonist subtype at screening (QD/BID formulations, QW formulations)] assigned by IRT will be summarized. The percentages will be calculated using the number of randomized patients as the denominator. The discrepancy between the strata assigned by IRT and the information reported on eCRF will be listed for all randomized patients.

Kaplan-Meier (KM) plots of the cumulative incidence of open-label IMP discontinuation due to any reason or due to AE will be provided for the 26-week randomized treatment period. Additionally, a listing of these patients, along with the reason for discontinuation, will be provided. Time to treatment discontinuation will be defined as the number of days from the first injection of open label IMP until the day of treatment discontinuation. All completers will be considered as censored observations. The censoring time will be the number of days from the first injection of open-label IMP until the last injection date during 26-week randomized treatment period. Similar KM plots and listing of patients will also be provided for the whole study including 26-week single-arm extension period (FRC group only).

All major or critical deviations will be listed and summarized in tables giving numbers and percentages of deviations by treatment group.

Additionally, the analysis populations for efficacy, safety defined in [Section 2.3](#) will be summarized in a table by number of patients on the randomized population:

- Efficacy population: modified intent-to-treat (mITT) population,
- Safety population.
- PK population.

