
STATISTICAL CONSIDERATIONS
	
Sample size determination:
 
A sample size of 250 patients per group will provide 90% power to detect a difference of 0.4% in the HbA1c change from baseline to Week 26 between the FRC and GLP-1 receptor agonist arm. This calculation assumes a common standard deviation of 1.1% at the 5% significance level (2-sided) and a common drop-out rate of 20% at 26 weeks. It is based on the intent-To-Treat (ITT) analysis and also assumes in the conservative manner that the FRC dropped patients will respond as the control patients, ie, no treatment difference between FRC dropped patients and the control patients.
 
Analysis population:
 
The primary efficacy population will be the modified Intent-To-Treat (mITT) population, which includes all randomized patients who have a baseline assessment and at least one post-baseline assessment of any primary or secondary efficacy endpoints, irrespective of compliance with the study protocol and procedures. Patients will be analyzed in efficacy analyses by the treatment regimen allocated by interactive response technology (IRT) according to the randomization schedule at randomization visit (as randomized).
 
The safety analysis will be conducted on the safety population, defined as all randomized patients exposed to at least one dose of investigational medicinal product, regardless of the amount of treatment administered. Patients will be analyzed according to the treatment regimen actually received.
 
Primary efficacy endpoint analysis:
 
Analyses of the primary efficacy endpoint (change from baseline to Week 26 in HbA1c) will be performed using the mITT population, using HbA1c values obtained from the scheduled visits during the 26-week randomized treatment period, including those obtained after IMP discontinuation or rescue medication use.
 
The statistical test will be two-sided at the alpha level of 0.05.
 
The primary analysis method for the primary efficacy endpoint will be a mixed-effect model with repeated measures (MMRM) under the missing at random framework. The MMRM model will include the treatment groups, randomization

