- For quantitative safety parameters based on central laboratory/reading measurements, descriptive statistics will be used to summarize results and change from baseline values by visit and treatment group. Summaries will include the last on-treatment value (see [Section 2.5.4](#));
- The analysis of the safety variables will be descriptive and no testing is planned;
- Selected safety analyses will be summarized by age group (<50, ≥50 to <65, ≥65 to < 75, ≥75 years of age), gender, race subgroups, GLP-1 receptor agonist subtype at screening, and any pertinent subgroups as appropriate.

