- All treatment-emergent SAEs by primary SOC, HLGT, HLT, and PT, showing the number (%) of patients with at least 1 treatment-emergent SAE, sorted by the internationally agreed SOC order. The other levels (HLGT, HLT, PT) will be presented in alphabetical order.

- All treatment-emergent SAEs regardless of relationship and related to IMP, by primary SOC, HLGT, HLT, and PT, showing the number (%) of patients with at least 1 treatment-emergent SAEs, sorted by the internationally agreed SOC order. The other levels (HLGT, HLT, PT) will be presented in alphabetical order.

Analysis of all treatment-emergent adverse event(s) leading to treatment discontinuation

- All TEAEs leading to treatment discontinuation, by primary SOC, HLGT, HLT, and PT, showing the number (%) of patients with at least 1 TEAE leading to treatment discontinuation, sorted by the internationally agreed SOC order. The other levels (HLGT, HLT, PT) will be presented in alphabetical order.

Local tolerability at injection site

The number (%) of patients with local intolerability at injection site will be summarized by PT (PTs coded from the investigator reported terms or PTs coded from ARAC diagnosis terms), sorted by decreasing incidence of PT. Similar summaries will be provided for FRC group respectively by anti-lixisenatide and anti-insulin glargine antibody status (Positive, Negative). All events will be listed.

Allergic reactions

Kaplan-Meier curves will be provided for the time to first onset of events adjudicated as allergic reactions by ARAC. The number (%) of patients with events adjudicated as allergic reactions by ARAC will be summarized by PT (sorted by decreasing incidence of PT) and ARAC diagnosis along with 2 subcategories, events adjudicated as possibly related to IMP and events adjudicated as not related to IMP. Tabulation summaries will be provided as necessary by gender (Male, Female), age group (<50, ≥50 to <65, ≥65 to <75, ≥75 years of age), race (American Indian or Alaska Native, Asian/Oriental, Black, Native Hawaiian or Other Pacific Islander, White, Other). Similar summaries will be provided for FRC group respectively by anti-lixisenatide and anti-insulin glargine antibody status (Positive, Negative).

All the allergic events reported by the investigator on the AE form for suspected allergic event and its associated complementary forms (confirmed or not confirmed by ARAC) will be listed.

Pancreatic-related events

- Increased pancreatic enzymes >2 times ULN

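### The Kaplan-Meier curve for IMP discontinuation due to AE has no stated rule for patients who stop for other reasons; if they are censored, it modestly overstates the cumulative incidence it is labelled as showing

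*SAP*

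**What the plan says.** SAP section 2.2 (Disposition of patients) plans "Kaplan-Meier (KM) plots of the cumulative incidence of open-label IMP discontinuation due to any reason or due to AE" for the 26-week randomized period. Similar plots are to cover the whole study for the FRC group alone. Event time runs from first injection to the day of discontinuation. On censoring, the SAP says "All completers will be considered as censored observations", and it sets the censoring time at the last injection in the 26-week period. It does not say how a patient who stops for a non-AE reason is treated in the due-to-AE curve, and it mentions no competing-risk estimator.

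Two crude summaries stand beside the plots. Section 2.2 adds that "Reasons for treatment discontinuation will be provided in tables giving numbers and percentages by treatment group", with randomized patients as denominator. Section 2.4.5.2 has a table "showing the number (%) of patients with at least 1 TEAE leading to treatment discontinuation" in the safety population. On inference, section 2.4.5 states: "The analysis of the safety variables will be descriptive and no testing is planned".

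The documents give no discontinuation rate by reason. The sample-size paragraph of the protocol synopsis assumes "a common drop-out rate of 20% at 26 weeks".

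**The concern.** A patient who has permanently stopped IMP for a non-AE reason can no longer stop it because of an AE. For the due-to-AE curve, that stop is a competing event. Such a patient is neither an event nor a completer, so the SAP's rule does not place them. The only censoring time given is the last injection date. Applied to these patients, it removes them from the risk set at about the day they stop, as though they could still have stopped for an AE later. One minus Kaplan-Meier then estimates what would be seen if no other discontinuation occurred, under independence of the two causes. That is not the cumulative incidence named in the SAP.

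What is at stake is the reading of a tolerability plot. Its end point could sit above the crude AE-discontinuation percentage in the same report with no explanation, and two programmers could draw different curves from the same text. The any-reason curve has no such problem.

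**Working it through.** **Inputs.** Total discontinuation T = 20% at 26 weeks is the documents' drop-out figure. SAP section 1.3 describes these FRC patients as having discontinued treatment, so using it as total IMP discontinuation is reasonable, but it remains an assumption. The share s of stops due to AE is not given; 10% to 90% is assumed.

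**The plan's own figure.** No AE-discontinuation figure is stated, so none can be reproduced. The sample size that uses the 20% does reproduce. The diluted difference is 0.4 × (1 − 0.20) = 0.32, and with SD 1.1, two-sided 5% and 90% power, n is 249 per group by normal approximation and 250 by t-test. The plan states 250.

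**Formulas.** Under proportional cause-specific hazards:
- cumulative hazard of any stop: H = −ln(1 − T)
- cumulative incidence of AE stops: T × s
- one minus Kaplan-Meier, other stops censored: 1 − exp(−sH) = 1 − (1 − T)^s

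**Results at T = 20%.**

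| AE share s | Cumulative incidence | 1 − KM | Overstatement (points) |
|---|---|---|---|
| 10% | 2.00% | 2.21% | 0.21 |
| 25% | 5.00% | 5.43% | 0.43 |
| 50% | 10.00% | 10.56% | 0.56 |
| 75% | 15.00% | 15.41% | 0.41 |
| 90% | 18.00% | 18.19% | 0.19 |

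A simulation of 1,000 trials' worth of one 250-patient arm at s = 50% gave 10.57% against 10.00%.

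**Event order.** If all AE stops come first, the overstatement is zero. If all other stops come first, 1 − KM = AE/(1 − other). For 10% AE and 10% other this is 0.10/0.90 = 11.11%, an overstatement of 1.1 points, which is about the maximum at T = 20%.

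**Other totals (assumed).** At T = 10% the overstatement is at most about 0.13 point across the same shares. At T = 30%, which might suit the 52-week FRC curve, it is about 0.5 to 1.3 points.

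**Between arms (assumed AE/other splits, T = 20% in each arm).**
- 5%/15% in both arms: bias 0.43 point in each, arm difference unaffected.
- 10%/10% against 5%/15%: biases 0.56 and 0.43, so the difference reads 5.13 points instead of 5.00.
- 10%/10% against 2%/18%: biases 0.56 and 0.21, so the difference reads 8.35 points instead of 8.00.

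**The case against.** **Censoring of non-AE stoppers is inferred.** This stands. The SAP names only completers. If non-AE stoppers were instead kept event-free to the end of the 26-week period, one minus Kaplan-Meier would equal the cumulative incidence. What the text shows for certain is a missing rule; the bias follows from the usual way of filling it.

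**The right Week 26 figure is already planned.** This largely stands. With near-complete follow-up of treatment status, the crude percentages by reason estimate the Week 26 cumulative incidence, apart from randomized but untreated patients in the section 2.2 denominator. They do not correct the curve, and they help less for the whole-study FRC plot. There, section 2.2 tabulates reasons separately by period, and some patients may finish Week 26 without entering the extension (Protocol section 7.2.5).

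**Unequal bias.** A reader might infer that the curves distort the comparison of arms, for instance because control patients on a failing drug stop more often for non-AE reasons. The documents do not support this. They assume one common drop-out rate and give no split by reason and arm. Protocol section 8.2.3 answers poor control with rescue therapy while study treatment continues, and section 10.3 treats permanent discontinuation as a last resort. Patients may still stop at any time (section 10.3.3), and the arms do differ: one continues a familiar drug, the other starts a new one, without blinding. Unequal bias is therefore possible but not shown.

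Even an assumed split well away from the common 20% has a small effect. Take AE stops of 8% in both arms and other stops of 4% against 20%. The curves then end at 8.17% and 8.96%, a false gap of 0.8 point. The standard error of the difference at 250 per arm is √(2 × 0.08 × 0.92/250) = 2.4 points. The whole-study curve covers FRC only, so it cannot distort an arm comparison.

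**Conclusion.** The point holds as a minor one. The SAP calls the due-to-AE curve a cumulative incidence, uses an estimator that does not deliver one if non-AE stops are censored, and leaves their handling unstated. At 20% total discontinuation the overstatement is about 0.2 to 0.6 point (1% to 10% in relative terms), and 0 to about 1.1 points over all orderings of events. This rests on the 20% drop-out being total IMP discontinuation, on the assumed AE shares, on proportional hazards for the central range, and on censoring at the stop date. A difference in bias between arms is conditional on rates or timing that the documents do not supply. The plots carry no test, and neither the primary analysis nor the tested secondary endpoints use them.

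**What to change.** In SAP section 2.2, estimate the due-to-AE curves (26 weeks, and whole study for FRC) with the Aalen-Johansen cumulative incidence function, treating non-AE discontinuation as a competing event. In the whole-study curve, censor Week 26 completers who do not enter the extension at their last injection. Keep Kaplan-Meier for discontinuation due to any reason.

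The reason for discontinuation is already collected and listed, so no new data are needed. The cost is a sentence or two in the SAP and a small programming change.

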2.2.1 Randomization and drug dispensing irregularities

Randomization and drug-dispensing irregularities occur whenever:

1. A randomization is not in accordance with the protocol-defined randomization method, such as a) an ineligible patient is randomized, b) a patient is randomized based on an incorrect stratum, c) a patient is randomized twice, or d) in a dynamic randomization scheme the treatment assignment is, in fact, not random, due to a computer program error.

OR

2. A patient is dispensed an IMP kit not allocated by the protocol-defined randomization, such as a) a patient at any time in the study is dispensed a different treatment kit than as randomized (which may or may not contain the correct-as-randomized IMP), or b) a nonrandomized patient is treated with IMP reserved for randomized patients.

Randomization and drug-dispensing irregularities will be monitored throughout the study and reviewed on an ongoing basis.

All randomization and drug-dispensing irregularities will be documented in the CSR. If the number of irregularities is large enough to make a tabular summary useful, the irregularities will be categorized and summarized among randomized patients (number and percentages). Nonrandomized, treated patients will be described separately.

2.3 ANALYSIS POPULATIONS

Patients treated without being randomized (patients who received open-label IMP without calling the IRT or before calling the IRT, or patients who did not give their informed consent) will not be considered as randomized. They will be excluded from any population for analysis, including efficacy and safety. However, if these patients experience any safety event, they will be presented and listed separately in the appendix of the CSR.

The randomized population includes any patient who has been allocated to a randomized treatment regardless of whether the treatment kit was used.

For any patient randomized more than once, only the data associated with the first randomization will be used in any analysis population. The safety experience associated with any later randomization will be assessed separately.

The safety experience of patients treated and not randomized will be reported separately, and these patients will not be in the safety population.

2.3.1 Efficacy populations

The mITT population will be the primary population for efficacy analyses. For efficacy analyses, patients will be analyzed in the treatment group to which they were randomized by the IRT, irrespective of the treatment actually received.

2.3.1.1 Modified intent-to-treat population

The mITT population consists of all randomized patients who have both a baseline assessment and at least 1 post-baseline assessment of any primary or secondary efficacy variables, irrespective of compliance with the study protocol and procedures. Patients will be analyzed for efficacy analyses according to the treatment group to which they are randomized.

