1.3 DETERMINATION OF SAMPLE SIZE

[figure not shown]
The sample size calculations are based on the primary efficacy variable change in HbA1c from baseline to Week 26 and ITT analysis, with the following assumptions:

- A common standard deviation of 1.1%,
- A 0.4% mean difference between FRC and GLP-1 receptor agonist in change in HbA1c from baseline to Week 26,
- A drop-out rate of 20%. The patients in the FRC group who discontinued treatment are assumed to respond the same as the control patients, i.e., no treatment difference between the patients in the FRC group who discontinued treatment and the control patients
- A t-test at a 2-sided 5% significance level with at least 90% power.

Based on the above assumptions, 500 patients (250 per group) are needed for this study.

Calculations were made using nQuery Advisor® 7.0.

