2.4.4 Analyses of efficacy endpoints

Efficacy analyses will be performed on the mITT population using efficacy assessment collected during the study, including those obtained after IMP discontinuation or introduction of rescue therapy, unless otherwise specified.

For a patient to be included in a change from baseline analysis (endpoint – baseline) or a baseline adjusted analysis of an endpoint, the patient must have both a baseline and a post-baseline measure for that endpoint.

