Summary statistics (for screening value, baseline value, observed values, and observed changes from baseline) at scheduled visits (using OC) will be provided for each treatment group for continuous secondary efficacy endpoints. Each summary will include the number of observations, mean, SD, SE, minimum, median, and maximum. Graphical presentations will also be used to examine trends over time using mean values (±SE) and mean changes from baseline (±SE) at each of the scheduled visits (using OC).

All categorical secondary efficacy endpoints defined for 26-week randomized treatment period in [Section 2.1.3.2](#) will be analyzed using a Cochran-Mantel-Haenszel (CMH) method stratified on randomization strata of HbA_{1c} (<8%, ≥8%) at visit 1(week -2) and randomization strata of GLP-1 receptor agonist subtype (QD/BID formulations, QW formulations) at screening. The proportion in each treatment group will be provided, as well as the difference of proportions between groups

with associated 2-sided 95% CI. For the categorical secondary endpoints in which HbA1c is assessed at Week 26, all values at Week 26 will be used to determine whether a patient is a responder or not, even if they are measured after IMP discontinuation or introduction or rescue therapy. If no assessment is available at Week 26 at all, patients will be treated as failures (non-responders).

For HbA1c responders ($\leq 6.5\%$, $< 7\%$), summary tables and graphs will be provided by treatment group at scheduled visits (using OC). For between-group comparison, a sensitivity analysis will be performed excluding patients whose HbA1c values at baseline are $\leq 6.5\%$ (for the $\leq 6.5\%$ responder analysis) or $< 7\%$ (for the 7% responder analysis). The summary by visit may also be provided excluding those patients.

A KM curve will be provided by treatment group for the cumulative incidence of rescue therapy during the 26-week randomized treatment period and during the whole study period including the extension period (FRC group only). A listing will be provided for rescued patients.

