For all continuous secondary endpoints, only descriptive statistics will be provided for the FRC group at the scheduled visits for the whole study period including the extension period. For all the categorical secondary endpoints defined for the extension period, counts and percentages will be summarized for FRC group using all data available at Week 52, with patients having data missing at Week 52 treatment as non-responders.

Sensitivity analysis

Sensitivity analyses will be performed for the following variables using scheduled measurements collected during the 26-week on-treatment period (excluding those collected after introduction of rescue therapy) (see [Section 2.1.3](#)). Continuous variables will be analyzed using MMRM or ANCOVA depending on the variables as specified earlier in [Section 2.4.4.2](#). Categorical variables will be analyzed using CMH method as described earlier. For the categorical variables in which HbA1c is assessed at Week 26, patients will be treated as failures (non-responders) if they have no assessment during the on-treatment period, including those who discontinue study treatment before Week 26, start rescue therapy before Week 26, or have no on-treatment assessment at all in mITT population.

- Change in 2-hour PPG and in glucose excursion during the standardized meal test from baseline to Week 26,
- Change in the daily average of the 7-point SMPG from baseline to Week 26 (each time point and average daily value),
- Change in FPG from baseline to Week 26,
- Change in body weight from baseline to Week 26,
- Percentage of patients reaching HbA1c $\leq 6.5\%$ at Week 26,
- Percentage of patients reaching HbA1c $< 7\%$ at Week 26.

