2.4.4.3 Multiplicity issues

To control the Type I error, a step-down testing procedure (please see [Figure 1](#)) will be applied.

[figure not shown]
For the primary efficacy endpoint (change from baseline to Week 26 in HbA_{1c}), no multiplicity adjustment is needed to control the Type I error since only one comparison of FRC versus GLP-1 receptor agonist will be performed.

If the primary variable is statistically significant at the 5% level, a hierarchical testing procedure will be performed to test the following secondary efficacy variables in the following prioritized order. Testing will stop when an endpoint is found not to be statistically significant at the 5% level:

1. Percentage of patients reaching HbA_{1c} <7% at Week 26.
2. Change in FPG from baseline to Week 26.
3. Change in the daily average of the 7-point SMPG from baseline to Week 26.
4. Change in 2-hour Post Prandial Glucose (PPG) and/or glucose excursion during the standardized meal test from baseline to Week 26.

Multiplicity adjustment will not be performed on the secondary efficacy variables that are not included in the above list.

Figure 1 - The step-down testing procedure

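### The HbA1c responder tests leave out randomised patients with no post-baseline efficacy value, whom the plan's own missing-data rule would score as failures; the effect is probably small and is cheap to remove

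*SAP*

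**What the plan says.** SAP 2.4.4 sets the population for efficacy: "Efficacy analyses will be performed on the mITT population using efficacy assessment collected during the study", unless otherwise specified. SAP 2.3.1.1 limits that population to randomised patients "who have both a baseline assessment and at least 1 post-baseline assessment of any primary or secondary efficacy variables"; Protocol 11.3.1.1 has the same rule.

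The categorical secondary endpoints, including HbA1c <7% and ≤6.5%, "will be analyzed using a Cochran-Mantel-Haenszel (CMH) method stratified on randomization strata" (SAP 2.4.4.2). No other population is named for them. The same section handles missing data as follows: "If no assessment is available at Week 26 at all, patients will be treated as failures". Nothing extends this to randomised patients outside mITT. The on-treatment sensitivity analysis confines its parallel failure rule explicitly, ending with patients who "or have no on-treatment assessment at all in mITT population".

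In SAP 2.4.4.3, "Percentage of patients reaching HbA_{1c} <7% at Week 26" is the first secondary endpoint tested after the primary, and "Testing will stop when an endpoint is found not to be statistically significant at the 5% level". Neither document plans a responder analysis on all randomised patients.

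**The concern.** A responder endpoint with a missing-equals-failure rule needs no post-baseline value: every randomised patient can be classified. Requiring one splits patients with the same outcome into two groups. Someone who leaves after a single Week 4 weight is counted as a failure; someone who leaves earlier with no value is not counted at all. Both lack a Week 26 HbA1c.

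For the continuous endpoints the requirement costs nothing, because SAP 2.4.4 already demands a baseline and a post-baseline value of the endpoint itself. Its effect falls on the responder endpoints, where it is not needed.

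At stake are the stated response rates, their difference and, in a close result, the step 1 test on which the later secondary tests depend. The trial is open-label; one arm stops its existing GLP-1 receptor agonist and starts a titrated injection, while the other continues unchanged. Very early loss could therefore depend on allocation.

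**Working it through.** **1. Who is excluded.** In the Protocol 1.2 flow chart, the first scheduled post-baseline efficacy values are body weight and FPG at Week 4 (V11). HbA1c follows at Week 8 and the 7-point SMPG profile at Week 12. Any one of these keeps a patient in mITT. HbA1c is itself the primary variable, so a patient excluded for having no post-baseline value necessarily has no Week 26 HbA1c and would be a failure under SAP 2.4.4.2.

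**2. The plan's own figure.** The documents give no power, sample size or expected rate for the responder test. The only figure to reproduce is the primary-endpoint sample size (SAP 1.3: SD 1.1%, difference 0.4%, 20% drop-out responding as control, two-sided 5%, 90% power). The diluted effect is 0.4 × (1 − 0.20) = 0.32. Then n = 2 × (1.960 + 1.282)² × 1.1² / 0.32², which gives 249 per group against 250 stated. With 250, power is 90.2%. The figure reproduces.

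**3. Formula.** With x responders among n randomised and m excluded, the mITT rate is x/(n − m) and the all-randomised rate is x/n. The ratio is n/(n − m). For n = 250 this is 1.008 at m = 2, 1.020 at m = 5 and 1.050 at m = 12. Equivalently, all-randomised rate = mITT rate × (1 − fraction excluded).

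**4. Size.** Assumed mITT rates are 60% FRC v 25% control, a difference of 35.0 points. Neither these rates nor the exclusion fractions come from the documents.

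| Excluded, FRC v control | All-randomised difference (points) |
|---|---|
| 3% v 3% | 60 × 0.97 − 25 × 0.97 = 33.95 |
| 3% v 1% | 60 × 0.97 − 25 × 0.99 = 33.45 |
| 4% v 1% | 60 × 0.96 − 25 × 0.99 = 32.85 |
| 1% v 3% | 60 × 0.99 − 25 × 0.97 = 35.15 |

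Equal losses still move the difference, by about 1 point at 3% per arm, because the higher rate is scaled up more. With excluded fractions a (FRC) and b (control), the mITT difference is too large when 60a > 25b. At these rates mITT understates the difference only if control loses more than 60/25 = 2.4 times as many.

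A second illustration uses rates near the 55% v 30% that Protocol section 4 quotes from an earlier FRC study in a different population. Take 138/250 v 75/250, or 55.2% v 30.0% (25.2 points), on all randomised. In mITT the difference becomes 25.7 points with 5 excluded per arm, 26.5 with 12 per arm, and 27.7 with 12 FRC v 2 control.

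**5. Effect on the test** (unstratified two-proportion z-test, 250 randomised per arm).

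- Large difference: in the 4% v 1% scenario the all-randomised rates are 57.6% v 24.75%, pooled 0.41175. The standard error is √(0.41175 × 0.58825 × 2/250) = 0.0440, so z = 0.3285/0.0440 ≈ 7.5. The verdict is unaffected. None of the scenarios run at 55.2% v 30.0% changes it either.
- Near-borderline: with 100/250 v 80/250 (40% v 32%), p = 0.062 on all randomised. In mITT, p = 0.061 with 5 v 5 excluded, 0.045 with 5 v 1 and 0.026 with 12 v 2.
- Type I error: with a true all-randomised rate of 40% in both arms (400,000 simulations, fixed exclusions), the two-sided error is about 0.049 for 5 v 5, 0.054 for 5 v 1 and 0.064 for 12 v 2.

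**The case against.** The strongest reply is that the excluded group is very small. mITT accepts any post-baseline efficacy value, not only HbA1c. Patients who stop treatment should have the V28 assessments as soon as possible and then stay in the study (Protocol 10.3.4). Patients who withdraw from the study are assessed with the end-of-study procedures if possible (Protocol 10.3.5). Most early leavers therefore remain in mITT and are already scored as failures. Rescue use is itself a secondary endpoint (SAP 2.1.3.2); if it counted as a post-baseline assessment, still fewer would be lost, but the SAP does not settle this. The mITT counts will be reported by arm against the number randomised (Protocol 11.2), so a reader could rebuild the all-randomised rates. All of this stands and limits the size. It does not supply a reason for the exclusion, and a rebuilt rate is not the planned test.

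Three stronger readings are tempting but not supported.

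- A reader might infer that early leavers in general are dropped. The any-variable rule and the exit visits rule that out.
- A reader might infer that the bias must favour FRC. Nothing in the documents predicts which arm loses more patients before Week 4, and the 1% v 3% case goes slightly the other way.
- A reader might infer that the plan contradicts its own denominator because "The sample size calculations are based on the primary efficacy variable change in HbA1c from baseline to Week 26 and ITT analysis". That sentence concerns the primary continuous endpoint and sets no denominator for the responder test.

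**Conclusion.** The point holds on the text and is limited in size. The upward shift in an arm's rate is certain whenever a patient is excluded for this reason, since each would be a failure under the plan's own rule. How many there will be is unknown: the documents give only an overall 20% drop-out. Under assumed exclusions of 1% to 4% per arm and mITT rates of 60% v 25%, the all-randomised difference lies between 32.85 and 35.15 points, against 35.0 in mITT.

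A reader might go further and infer that the step 1 result, and so the later secondary tests, is at risk. The calculations do not show that at the rates assumed. A changed verdict needs a result close to 5% and, for exclusions of any plausible size, exclusions that differ by arm. Open-label allocation makes unequal loss possible, not established. This is an inexpensive improvement to a hierarchical endpoint, and it does not threaten the trial's conclusions.

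**What to change.** In SAP 2.4.4.2 and Protocol 11.4.4.2, state that the HbA1c <7% and ≤6.5% Cochran-Mantel-Haenszel analyses use all randomised patients, as randomised, with a missing Week 26 HbA1c scored as non-response. Keep the mITT version as a supportive table and report the number excluded from mITT by arm beside it. The MMRM analyses need no change.

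The cost is one sentence in each document and no new data. The downside is that the stated response rates become slightly lower.
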